- To evaluate the efficacy and safety of human insulin (regular insulin and intermediate acting NPH insulin)
- To assess the efficacy and safety of insulin analog (basal insulin glargine and rapid acting insulin aspart)
- To compare the efficacy and safety of two insulin regimen
- To evaluate the socio-demographic and clinical characteristics of the patients included in two treatment arms

METHODOLOGY:

Type of study: Single-center, open-label, randomized trial

Place of Study: Department of Neurology, National Institute of Neurosciences & Hospital, Dhaka.

Study Period: February to June, 2021

Study population: Patients admitted in the Department of Neurology with acute stroke and hyperglycemia

Sample Size:

Sample size was calculated according to following formula for non-inferiority trial (17):

$$N = 2 \times \left(\frac{Z_{1-\alpha} + Z_{1-\beta}}{\delta_0} \right)^2 \times S^2$$

Here, N= sample size per group

$$\alpha = 0.05$$

$$\beta = 0.20$$

δ_0 = a clinically acceptable margin (assumed as 3 mmol/L of blood glucose)

S² = Pooled standard deviation of both comparison group = 8

So,

$$N_{\text{non-inferiority}} = 2 \times \left(\frac{1.645 + 0.845}{3} \right)^2 \times 6^2 = 50$$

As a result, 50 patients will be randomly assigned to two treatment groups (50 human insulin regimen, 50 analog insulin regimen).

Inclusion criteria

- Patients admitted to adult neurology ward with acute stroke with
- Patients having hyperglycemia (capillary blood glucose ≥ 10 mmol/L in 2 or more occasions or having history of treatment for DM)
- Patients with age of 18-80 years of both sexes
- Patients or their attendants giving consent to take part in the study

Exclusion Criteria

- Patients with hyperglycemic emergencies (hyperglycemic hyperosmolar state or diabetic ketoacidosis)
- Pregnant patients
- Those not giving consent to participate in the study

Study Procedure

Patients will be randomly assigned to receive either a human insulin regimen (starting with regular insulin three times a day with NPH insulin twice a day) or analog insulin regimen (basal insulin glargine once daily and insulin aspart three times a day) following a computer-generated randomization table. All oral antidiabetic drugs will be discontinued on admission.

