For a patient who is known to have diabetes but were not getting insulin previously (or previous insulin dosage is not known), insulin therapy will be started at a total daily dose of 0.3-0.4 units/kg/day for an admission BG between 10-15 mmol/L or 0.5-0.6 units/kg/day for a BG >15 mmol/L. In previously insulin treated patients, ongoing total daily dose of insulin will be started. If there is history of poor glycemic control with ongoing insulin dose, then 10-20% increase of daily dose of insulin will be considered.

For a patient who is not known to have diabetes, insulin therapy will be started if admission BG is >10 mmol/L in two or more occasions. A total daily dose of 0.3-0.4 units/kg/day will be started if admission BG is 10-15 mmol/L and 0.5-0.6 units/kg/day for a BG >15 mmol/L.

Patients treated with human insulin regimen will receive 50% of total daily dose as NPH insulin at around 6 am and 6 pm, while the rest 50% regular human insulin three times a day in 3 equally divided doses at around 6 am, 12 pm and 6 pm.

Patients treated with modern insulin regimen will receive 50% of total daily dose as basal insulin glargine at the same time of day and 50% as insulin aspart given in 3 equally divided doses at 6 am, 12 pm and 6 pm.

In both groups, insulin dosage will be adjusted daily to a target fasting and premeal BG 7.8-10.0 mmol/L in the absence of hypoglycemia. Insulin dosage will be adjusted daily according to BG values. If the fasting and/or premeal BG is 10-15 mmol/L in the absence of hypoglycemia, the total daily dose will be increased by 10% every day. If the fasting and/or premeal BG is >15 mmol/L, the insulin daily dose will be increased by 20% every day. If a patient develops hypoglycemia (BG <3.9 mmol/L), the insulin daily dose will be decreased by 20%. Supplemental regular insulin will be given in addition to scheduled mealtime insulin for BG >10 mmol/L using a supplemental insulin protocol.

BG will be measured before each bolus insulin injection (at 6 am, 12 pm and 6 pm). Glycated hemoglobin (HbA1c) will be measured after hospital admission if not done within last three months.

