Except anti-diabetic treatment, other treatments will be continued as per the decisions of the treating physicians. If NG feeding is discontinued and patient is kept NPO, conventional group will receive neutralizing insulin with any dextrose containing fluid along with low dose NPH insulin, if needed. Modern insulin group will receive neutralizing insulin with any dextrose containing fluid with glargine insulin as before.

After recruitment, each recruited patient will be visited daily (even in holidays according to a predefined schedule) by one of the investigators and insulin dose will be adjusted according to glucose profile of previous day. Insulin injection and capillary blood glucose monitoring by glucometer will be done by trained nurses as part of their routine patient care. Doctors and nurses on duty will be provided with cell number of the investigators who will receive call on 24/7 basis for any emergency or uncertainty regarding management of hyperglycemia.

Hypoglycemia is regarded as the only short-term adverse event of insulin. As both treatment arms will use established and recognized insulin regimen, no compensation will be provided to the patient or his/her attendants in case of any adverse event. As most of the hospitalized patients have severe stroke with case fatality rate around 20%, death will not be regarded as parameter of primary treatment outcome.

During discharge, last in-hospital insulin dose will be continued with education to the caregiver regarding insulin injection and glucose monitoring technique. No follow up visit is included in the study.

Protocol deviation and protocol violation:

Deviation to protocol will be recorded and reported to ethical committee as soon as possible. Failure to obtain informed written consent, use of incorrect insulin regimen, not fulfilling inclusion and exclusion criteria will be regarded as protocol violation and will be reported to ethical committee immediately. In case of protocol violation, the data of related participant will be discarded.

Outcome variables

The primary efficacy outcome of the study will be the differences in glycemetic control between groups, as measured by mean daily BG concentration during the hospital stay.

The primary safety outcome will be the frequency of hypoglycemic events (BG <3.9 mmol/L).

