Secondary outcomes include differences between treatment groups in any of the following measures: total daily dose of insulin, length of hospital stay, hospital complications, and mortality.

Data collection technique

Data will be collected in a predesigned questionnaire by the research team. The researchers will recheck randomly and blindly to verify the collected data.

Data management

All data will be compiled and edited meticulously by thorough checking and rechecking. All omissions and inconsistencies will be corrected and will be removed methodically.

Statistical analysis

Computer based statistical analysis will be carried out with appropriate techniques and systems by SPSS 22.0. Quantitative data will be expressed as mean and standard deviation or median and inter-quartile range; and qualitative data will be expressed as frequency and percentage. Continuous variables, analysis will be made by the Students T-test or Mann-Whitney *U* test. Categorical variables will be analyzed by the χ^2 test. All probabilities will be 2-tailed. Statistical significance will be accepted at $p \leq 0.05$.

Utilization of results

The result of study will be helpful for the physicians to choose appropriate insulin regimen in patients hospitalized with acute stroke having hyperglycemia. It will also help the policy makers in ensuring adequate supply of appropriate insulin that may help improve the outcome of patients.

FLOW CHART

Sl. No.	Job Title	Feb'21	Mar'21	Apr'21	May'21	Jun'21
1.	Questionnaire Validation	√				
2.	Data Collection	√	√	√		
3.	Data Analysis				√	
4.	Report writing and Printing				√	√
5.	Submission					√

ETHICAL IMPLICATIONS:

Prior to the commencement of this study, approval of the institutional review board (IRB) of National Institute of Neurosciences & Hospital, Dhaka will be sought. The aims and objectives of the study along with its procedure, risks and benefits of this study will be explained to the patients or attendants of the patients in easily understandable local language and then written consent will be taken from each. It will be assured that all information and records would be kept confidential.

Role of funding agency

The funding agency will have no role in protocol development, data collection, analysis, interpretation or writing the report. The authors will have full access to all study data and will have the final responsibility for the decision to submit for publication.

REFERENCES:

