Abstract for IRB/Ethical Committee:

Glycemic control in acutely ill stroke patients with hyperglycemia is vital. Although insulin is the choice of anti-diabetic agent during acute stage, it is not clear which insulin regimen is better in terms of glycemic control and prevention of hypoglycemia in hospitalized acute stroke patients who are usually on small frequent nasogastric tube feeding. The present study aims to evaluate the efficacy and safety of human insulin (regular insulin and neutral protamine hagedorn, NPH insulin) to analog insulin (basal insulin glargine and rapid acting insulin aspart) in hospitalized acute stroke patients with hyperglycemia. In this single-center, open-label, randomized trial, 100 patients with acute stroke and hyperglycemia (capillary blood glucose ≥ 10 mmol/L on 2 or more occasions) or history of type 2 DM admitted in the in-patient Department of Neurology, National Institute of Neurosciences (NINS) & Hospital will be randomly assigned to receive human insulin or modern insulin therapy in 1:1 ratio. The study will be carried out from February to June 2021. Blood glucose (BG) will be monitored by standardized glucometer thrice a day and insulin dose will be adjusted daily. The primary outcome of the study will be the differences in glycemic control between groups, as measured by mean daily BG concentration during the hospital stay. Secondary outcomes include differences between treatment groups in any of the following measures: number of hypoglycemic events (BG < 3.9 mmol/L), total daily dose of insulin, length of hospital stay, hospital complications and mortality. Computer based statistical analysis will be carried out by SPSS 22.0. Quantitative data will be expressed as mean and standard deviation or median and inter-quartile range; and qualitative data will be expressed as frequency and percentage. Continuous variables will be compared by the Students T-test or Mann-Whitney *U* test. Categorical variables will be analyzed by the χ^2 test. All probabilities will be 2-tailed. Statistical significance will be accepted at $P \leq 0.05$. Prior to the commencement of this study, approval of the institutional review board (IRB) of NINS will be sought. The aims and objectives of the study along with its procedure, risks and benefits of this study will be explained to the patients or attendants of the patients in easily understandable local language and then written consent will be taken from each. The result of the study may help us to choose appropriate insulin regimen for hospitalized acute stroke patients in our setting.

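### The primary comparison of mean daily blood glucose is unadjusted, although the plan already collects baseline glucose and HbA1c; pre-specified adjustment costs almost nothing and is likely to gain precision

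*Combined protocol and SAP*

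**What the plan says.** Outcome variables (Section-C, Methodology) defines the primary efficacy outcome as the difference in glycemic control between arms, "as measured by mean daily BG concentration during the hospital stay".

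Statistical analysis gives one rule for all continuous outcomes: "Continuous variables, analysis will be made by the Students T-test or Mann-Whitney" U test, followed by "All probabilities will be 2-tailed". The Abstract for IRB/Ethical Committee in Section-E repeats it: "Continuous variables will be compared by the Students T-test or Mann-Whitney" U test. No covariate, regression model or analysis of covariance appears anywhere. The randomization is described only as a computer-generated table, with no stratification by baseline glycemia.

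Study Procedure plans the measurements that could serve as covariates:

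- "BG will be measured before each bolus insulin injection (at 6 am, 12 pm and 6 pm"). This includes the first bolus.
- "Glycated hemoglobin (HbA1c) will be measured after hospital admission if not done within last three months".

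The same section says that in both arms "insulin dosage will be adjusted daily to a target fasting and premeal BG 7.8-10.0 mmol/L in the absence of hypoglycemia".

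**The concern.** Baseline glycemia is an obvious candidate predictor of mean BG over a hospital stay. The plan measures it, but neither the randomization nor the analysis uses it. If baseline BG and HbA1c explain part of the between-patient variation in the outcome, an unadjusted test leaves that part in the error term. The confidence interval is then wider than the same data allow. With 50 patients per arm, a chance imbalance in starting glycemia also goes uncorrected.

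This is a matter of efficiency. Under randomization the unadjusted comparison is unbiased and its error rate is sound. Pre-specification matters because the trial is open-label: covariates chosen after results are seen would invite doubt.

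Two definitions are also missing, and adjustment needs both. No single baseline BG is defined. The outcome wording does not say whether readings before the first study insulin dose count in the mean.

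**Working it through.** **Inputs from the documents.** 50 patients per arm. Sample Size gives 3 mmol/L as "a clinically acceptable margin (assumed as 3 mmol/L of blood glucose"). The SD is 6 in the worked formula, although the accompanying text says 8. The sample size uses one-sided 0.05 (z = 1.645), and Statistical analysis uses two-sided tests.

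**Input that must be assumed.** r is the joint (multiple) correlation of baseline BG and HbA1c with mean daily BG. The documents give no value, so the range used is 0.2, 0.3, 0.5 and 0.6.

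**Step 1: the plan's own figure.** 2 × ((1.645 + 0.845)/3)² × 6² = 2 × 0.6889 × 36 = 49.6, rounded up to 50 per arm. It is reproduced with SD 6 and one-sided 0.05.

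**Step 2: unadjusted precision.** SE = SD × √(2/50) = 0.2 × SD = 1.20 mmol/L at SD 6. The 95% half-width is 1.96 × 1.20 = 2.35 mmol/L. With 3/1.20 = 2.5, power is Φ(2.5 − 1.960) = 70.5% two-sided and Φ(2.5 − 1.645) = 80.4% one-sided. Because 3 mmol/L is a non-inferiority margin, the 70.5% is the chance that a 95% interval stays inside the margin when the true difference is zero. Superiority power at a true difference of 3 mmol/L has the same value.

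**Step 3: adjusted precision.** Residual SD = 6 × √(1 − r²), put into the formulas of Step 2. The last column uses the noncentral t distribution and charges for two covariates: 96 degrees of freedom, with the variance multiplied by 1 + 2/95 = 1.021. The unadjusted entry in that column has 98 degrees of freedom and no penalty.

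| r | Residual SD | 95% half-width (mmol/L) | One-sided 0.05 power | Two-sided 0.05 power | Two-sided power, t with covariate penalty |
|---|---|---|---|---|---|
| unadjusted | 6.00 | 2.35 | 80.4% | 70.5% | 69.7% |
| 0.2 | 5.88 | 2.30 | 81.8% | 72.3% | 70.5% |
| 0.3 | 5.72 | 2.24 | 83.5% | 74.6% | 72.8% |
| 0.5 | 5.20 | 2.04 | 89.3% | 82.3% | 80.7% |
| 0.6 | 4.80 | 1.88 | 93.1% | 87.8% | 86.5% |

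A simulation of 20,000 trials per value of r gives 70.5%, 72.7%, 80.7% and 86.6%, in agreement with the last column.

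**Step 4: the downside.** Adjustment breaks even when 1 − R² = 1/1.021, that is R² = 2/97 = 0.021, or r of about 0.14. If the covariates explain nothing, two-sided power falls from 69.7% to 68.8%.

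**Step 5: the other stated SD.** At SD 8 the unadjusted SE is 1.60, and two-sided power (normal approximation) is Φ(3/1.60 − 1.960) = 46.6%. It rises to 48.2%, 50.2%, 58.1% and 64.9% over the same range of r.

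**The case against.** The strongest objection is that nothing here is wrong with the plan. An unadjusted comparison of randomized arms is a legitimate primary analysis, and the claimed benefit rests on a correlation the documents do not supply. Several features of the plan could make that correlation small:

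- Starting doses rise with admission BG for many patients.
- Doses are titrated daily towards a common range, with supplemental insulin above 10 mmol/L.
- One eligibility route restricts the BG range from below.
- Steroids, tube dislodgement and periods without feeding add variation that baseline values need not predict.

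At r = 0.2 the penalised gain is under one point, and at 0.3 about three. If the SD of patient means were well below 6, there would be little power to gain. At an assumed SD of 4, unadjusted two-sided power is already Φ(3/0.8 − 1.96), about 96%.

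Availability of the covariates is also inferred. HbA1c has no stated timing beyond after admission, may be up to three months old, and could be missing after an early death. Glucose readings are tied to bolus injections, so a reading before a first basal dose is not strictly guaranteed.

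Most of this stands, and it limits how large a gain can be promised. It does not count against the change itself. The worst case costs about one point of power, and the remaining gaps close with a definition of baseline BG and a rule for missing values. There is also an argument for a useful correlation: doses move by 10% or 20% a day and the outcome averages the whole stay, so early days should still reflect starting glycemia.

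**Conclusion.** The concern holds, as a recommended improvement and not as a flaw in validity. The plan names only an unadjusted test for its primary outcome while collecting two plausible predictors of it. At SD 6 and 50 per arm, adjustment gives about 1 to 17 points of two-sided power for r between 0.2 and 0.6 (69.7% to between 70.5% and 86.5%, penalty included), against a loss of about 1 point if r is zero. The gain disappears only if R² is about 0.02 or less.

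These figures assume that the SD in the sample-size section is the between-patient SD of each patient's mean BG, and that r lies in the range shown. Adjustment does not settle the conflict between SD 6 and SD 8. Bringing a residual SD of 8 down to 6 would need r of about 0.66, since √(1 − 36/64) = 0.66. Nor does it settle the mismatch between a one-sided design and a two-sided analysis. Confidence in the size of the gain is moderate.

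**What to change.** In Statistical analysis, and in the matching sentence of the Abstract for IRB/Ethical Committee, state that:

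1. The primary analysis is a linear model (ANCOVA) of each patient's mean daily BG on treatment arm, with baseline BG and HbA1c as covariates. It is reported as the adjusted difference with its confidence interval, which can be read directly against the 3 mmol/L margin.
2. Baseline BG is the last reading before the first study insulin dose. Pre-treatment readings serve only as the covariate and do not enter the outcome mean.
3. Patients with missing HbA1c stay in the model under a stated rule, for example imputation of the baseline mean.
4. The unadjusted t-test is a sensitivity analysis.

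The cost is a few lines of analysis text and two degrees of freedom. SPSS 22 fits the model, and no new measurement or additional patient is needed. The wording should be fixed before outcome data are examined.

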In most instances in the hospital setting, insulin is the preferred treatment for hyperglycemia (8). Human insulin in the form of regular insulin and intermediate acting insulin (neutral protamine hagedorn; NPH) are the most common insulin used for glycemic control in people with diabetes. However, they may not mimic the physiological insulin secretion pattern properly. As a result, tight glycemic control often leads to hypoglycemia. To improve the pharmacokinetics of the insulin, minor structural alterations are made to produce analogs insulin that have similar pharmacodynamics properties. These include long acting basal insulin like insulin detemir, glargine and degludec and rapid acting prandial insulin like insulin lispro, aspart or glulisine. These modern insulins are costlier and availability is often limited.

An insulin regimen with basal, prandial, and correction components is the preferred treatment for non-critically ill hospitalized patients with good nutritional intake (9). Clinical guidelines from

professional organizations recommend the use of subcutaneous insulin in the form of basal-bolus regimen as the preferred therapy for glycemic control in hospitalized medical and surgical patients with type 2 diabetes mellitus (T2DM) (8,10,11). Sliding scale regular human insulin regimen or premixed insulin in acute setting is strongly discouraged by current recommendations (12). These recommendations are mainly based on studies done on patients taking three major meals.

Use of regular insulin thrice a day is a common practice in our setting mainly due to its simplicity and relevance to feeding practice in acute stroke patients. Nevertheless, this regimen is associated with limited therapeutic success because of the lack of basal insulin coverage. Adding a long acting basal insulin in the form of NPH or basal insulin analogs are often not introduced in-hospital settings due to fear of hypoglycemia (9). Modern basal insulin analogs may be superior in this respect as they have more physiological pharmacokinetic properties (13).

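### The primary glucose comparison is left open between the t-test and Mann-Whitney, although only a mean-based analysis can be read against the 3 mmol/L margin

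*Combined protocol and SAP*

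**What the plan says.** The Outcome variables section defines the primary efficacy outcome as the between-group difference in glycemic control, "as measured by mean daily BG concentration during the hospital stay".

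The Statistical analysis section has no text specific to that outcome. Its one sentence on continuous data reads "Continuous variables, analysis will be made by the Students T-test or Mann-Whitney" U test. The Abstract for IRB/Ethical Committee repeats it: "Continuous variables will be compared by the Students T-test or Mann-Whitney" U test. Neither place gives a normality criterion, another rule for choosing, or an effect estimate with a confidence interval. The summary measure is open in the same way: "Quantitative data will be expressed as mean and standard deviation or median and inter-quartile range". On inference the section adds "All probabilities will be 2-tailed" and sets the threshold at p ≤ 0.05.

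The Sample Size section is specific: "Sample size was calculated according to following formula for non-inferiority trial". It uses the formula for a difference in means with a margin of 3 mmol/L.

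**The concern.** The two tests answer different questions. The t-test concerns the difference in means. Mann-Whitney concerns whether values in one arm tend to exceed those in the other. They agree closely when the two distributions have the same shape and spread, and can part when they do not.

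Two things follow. First, the margin is a mean difference in mmol/L, and a Mann-Whitney p-value supplies nothing to compare with it. Second, the choice of test can change the conclusion. The trial is open-label, and under Study Procedure the investigators adjust doses daily from each patient's glucose values. The people who will report the result therefore know the data by arm, and nothing in the plan binds them to one test.

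A conventional normality check would not remove the problem. It would send skewed data to Mann-Whitney, which is where the two tests are most likely to disagree.

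**Working it through.** **Which scale the design uses.** Inputs from the Sample Size section: one-sided Z = 1.645, Z for power = 0.845, margin 3 mmol/L, SD 6 as used in the worked line.

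N = 2 × ((1.645 + 0.845)/3)² × 6² = 2 × 0.6889 × 36 = 49.6, rounded up to 50 per group.

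The plan's figure is reproduced, and it is a calculation on means. (The same section describes the SD as 8. That discrepancy is a separate matter, so both values are used below.)

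**Simulation inputs.** From the plan: 50 per arm, two-sided 0.05, SDs 6 and 8. Assumed: one mean BG value per patient, a true mean of 11 mmol/L in both arms, the distribution shapes, and all other SDs. Each case has 20,000 simulated trials, or 10,000 where marked *. The Monte Carlo standard error at a 5% rate is √(0.05 × 0.95/20,000) = 0.15 percentage points, or 0.22 with 10,000.

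**Rejection rate when the true means are equal**

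| Distributions in the two arms | t-test | Mann-Whitney |
|---|---|---|
| Identical, normal SD 6 | 5.1% | 5.0% |
| Identical, lognormal SD 3 | 5.1% | 4.9% |
| Identical, lognormal SD 6 | 5.3% | 5.3% |
| Normal, SD 6 vs 3 | 4.9% | 5.6% |
| Normal, SD 4 vs 2.5 * | 4.6-6.0% | 5.5% |
| Lognormal, SD 2.5 vs 2 * | 4.6-6.0% | 5.4% |
| Lognormal, SD 3.5 vs 3 * | 4.6-6.0% | 5.4% |
| Lognormal, SD 3 vs 2 | 5.1% | 7.1% |
| Gamma, SD 4 vs 2.5 * | 4.6-6.0% | 7.5% |
| Lognormal, SD 4 vs 2.5 | 5.0% (Welch) | 9.6% |
| Lognormal, SD 8 vs 6 | 4.8% | 10.1% |
| Lognormal, SD 6 vs 4 | 5.3% | 11.8% |
| Gamma, SD 6 vs 3 * | 4.6-6.0% | 15.4% |
| Lognormal, SD 6 vs 3 | 5.2% | 20.7% |

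The entry 4.6-6.0% is the range of the Student test over all cases in the * runs.

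**Reporting whichever test is significant.** With identical distributions the rate is 6.1% (normal SD 6), 6.3% (lognormal SD 3) and 7.2% (lognormal SD 6).

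**Choosing by a Shapiro-Wilk check in each arm** (4,000 trials per case). For lognormal SD 6 vs 3 the check sends 97% of trials to Mann-Whitney, and the overall rejection rate is 20.4%. For SD 8 vs 6 it sends all of them, and the rate is 10.4%.

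**Why the tests part.** A lognormal with mean m and SD s has median m/√(1 + (s/m)²).

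- SD 6: 11/√(1 + 36/121) = 11/1.139 = 9.66 mmol/L.
- SD 3: 11/√(1 + 9/121) = 11/1.037 = 10.61 mmol/L.

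With equal means, the more variable arm has the lower median, and Mann-Whitney responds to that. In this case the two tests disagree on significance in 18% of trials.

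**The case against.** Much of the case on the other side stands.

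A reader might infer that the false-positive rate will be two to four times the nominal 5%. The documents do not support that. Such rates need marked skew together with clearly unequal spread. The plan gives one pooled SD, no arm-specific SD and no shape. With symmetric data or small SD differences the excess is at most about one percentage point.

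A reader might also take the Introduction's remark that basal analogs may be superior because "they have more physiological pharmacokinetic properties" as a forecast of less spread in the analog arm. In context it concerns fear of hypoglycemia when a basal insulin is added. It says nothing about how patient means vary between patients. The Introduction also describes human insulin as nearly similar in efficacy and safety, and Study Procedure gives both arms the same glucose target and daily adjustment rules.

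Nor is Mann-Whitney invalid. When medians are 9.66 and 10.61 mmol/L the distributions do differ, and the test correctly rejects its own null hypothesis. It errs only if the question is the difference in means. A shift estimate in mmol/L can accompany a rank test, but it equals the mean difference only under extra assumptions such as a common shape, and the plan does not mention one.

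The text is silent on when the test is chosen, so it cannot be said that the plan defers the choice until the data are seen. The sentence is generic and also covers length of stay, where a rank test is sensible. Finally, with equal arms the Student and Welch tests differ by at most about 0.2 percentage points, so the unequal-variance form is a preference and not a correction.

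None of this closes the gap: no part of the documents names the test for the primary outcome.

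**Conclusion.** The point holds as a mismatch between design and analysis. The trial is sized on a difference in means with a 3 mmol/L margin, while the analysis text permits a test that does not estimate that difference and gives no rule for when to use it. This conclusion rests on the text alone and needs no simulation.

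The size of the false-positive effect depends on distributions that the documents do not give. It runs from almost nothing (identical or symmetric distributions, or similar SDs) to 15-21% in the skewed SD 6 vs 3 case, against about 5% for the t-test throughout. The upper figures are the unfavourable end of assumed scenarios. They show what an unfixed choice could do, not what this trial should expect.

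**What to change.** In Statistical analysis, and in the IRB abstract, name one primary efficacy analysis: the difference between arms in per-patient mean daily BG, by a t-test (preferably the unequal-variance form) or its covariate-adjusted equivalent. Report it in mmol/L with its confidence interval and read the interval against the 3 mmol/L margin. State that the test is not selected by a normality check. Keep Mann-Whitney as a labelled sensitivity analysis for the primary outcome, and for outcomes such as length of stay.

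The confidence level has to be stated, because the sample size uses one-sided 0.05 (a 90% two-sided interval) and the analysis text uses two-tailed 0.05 (a 95% interval). At the latter, SD 6 needs 2 × ((1.960 + 0.842)/3)² × 36 = 62.8, or 63 per group, and 50 per group has about 71% power.

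Naming the analysis costs a sentence or two and no extra data. The downside is slightly less power than a rank test if both arms share the same heavy skew.
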